**Objectives:****Primary**

- To assess the suitability of CPX-351 as first intensive therapy in older (age  $\geq$ 60 years) patients with AML based on safety and efficacy. The primary efficacy endpoint will be overall survival (OS). The primary safety endpoint will be 30-day mortality.

**Secondary**

- To assess efficacy by response (CR, CRp, CRI, and CR+CRp+CRI) rate, response duration, and Event Free Survival (EFS)
- To assess safety by 30-day mortality, serious adverse events (SAE) and adverse event frequency and severity
- To assess QOL using FACT-LEU
- To assess the relationship of cognitive function to outcome using the Blessed Orientation-Memory-Concentration Test and the Montreal Cognitive Assessment
- To confirm the safety of CPX-351 as a post-remission (consolidation) therapy
- To supplement efficacy assessment by determining the rate of morphologic leukemia-free state (MLFS)

**Study Design:**

This is an open label study to assess the safety and efficacy of CPX-351 as first intensive therapy in elderly (age  $\geq$ 60 years) patients with AML with companion cognitive function testing to determine whether this contributes to outcome in these patients. Patients may have received prior AML treatment with non-intensive regimens, e.g. hypomethylating agents, low-dose cytarabine, or lenolidomide, but may not have received intensive AML treatment with anthracyclines and/or infusional cytarabine prior to enrollment on this trial. The cohort will include 30 patients treated with single-agent CPX-351. These patients will be assessed for efficacy and safety. Quality of life will be assessed using the FACT-LEU in all patients. Cognitive function will be assessed using the Blessed Orientation-Memory-Concentration Test and the Montreal Cognitive Assessment.

---

Study enrollment is expected to be completed within approximately 2 years.

**Sample Size:****30 patients**

**Study Drugs:**

CPX-351 (cytarabine:daunorubicin) Liposome Injection is a liposomal formulation of a fixed combination of the antineoplastic drugs cytarabine and daunorubicin. The two drugs are present inside the liposome in a 5:1 molar ratio shown to act synergistically in pre-clinical studies. The liposome membrane is composed of a 7:2:1 molar ratio of distearoylphosphatidylcholine, distearoylphosphatidylglycerol and cholesterol.

CPX-351 is provided as a sterile, pyrogen-free, purple, lyophilized product in 50 mL glass, single-use vials. Each 50 mL vial after reconstitution contains 20 mL of CPX-351 (5 units/mL). Each unit (u) contains 1.0 mg cytarabine and 0.44 mg daunorubicin base in liposomes suspended in sucrose. Product is stored at 5° ± 3°C.

---

**Efficacy Variables & Analysis:**

- To assess the suitability of CPX 351 in older patients with AML and the relationship of cognitive function to outcome
- Response rate (CR, CRp, CRI, and CR+CRp+CRI), (morphologic, cytogenetic and molecular response)
- Response duration (relapse-free survival)
- EFS
- Evaluation of QOL of CPX treated patients
- Evaluation of relationship of cognitive function to outcome in treated patients

---

**Safety Variables & Analysis:**

Patients will be monitored for all clinical adverse events as well as laboratory evaluations.

- Induction Mortality: assessed at Day 30 and 60; therapies may be changed after 30 days.
- Serious Adverse Events
- Adverse Events: Grades 1-5 and Grades 3-5
- Laboratory Evaluations
  - Routine hematology (CBC+diff+Platelet count) and chemistry (with LDH)
  - Time to hematologic recovery and proportion with prolonged cytopenias ( $\geq$  56 days)
- Cardiac Evaluations
  - Cardiac AEs: Grades 1-5 and Grades 3-5
  - ECG changes (pre-dose for each course, and at the end of each course)
  - LVEF changes (pre and post treatment)

---

**Other Variables & Analysis:**

**Quality of Life Assessment:** FACT-Leu will be used to assess patients at the start of treatment and one month after treatment completion.

---

**Cognitive Assessment:** The Blessed Orientation-Memory-Concentration Test and the Montreal Cognitive Assessment Mini will be administered at the start of treatment and one month after completion of therapy.

**Cardiac Assessments:** All ECG and ECHO/cardiac MRI assessments will be obtained and read locally for patient care.

---

## ABBREVIATIONS

7+3	Seven days of continuous infusion of cytarabine at 100 mg/m  /day and three days of daunorubicin at 60 mg/m  /day
5+2	Five days of continuous infusion of cytarabine at 100 mg/m  /day and 2 days of daunorubicin at 60 mg/m  /day
ADR	Adverse Drug Reaction
AE	Adverse Event
AHD	Antecedent Hematologic Disorders
ALL	Acute Lymphocytic Leukemia
ALT	Alanine Transaminase (SGPT)
AML	Acute Myeloid Leukemia
ANC	Absolute Neutrophil Count
Ara-U	Arabinosyluracil
ASCO	American Society of Clinical Oncology
AST	Aspartate Transaminase (SGOT)
ATPase	Adenosine triphosphatase
AUC	Area under the plasma concentration-time curve
BID	Twice daily
BSA	Body Surface Area
BUN	Blood Urea Nitrogen
C	Celsius
Cmax	Maximum plasma concentration
CL	Clearance
CNS	Central nervous system
CPX-351	CPX-351 (cytarabine:daunorubicin) Liposome Injection
CR	Complete Remission
CRi	Complete Remission with incomplete hematologic recovery
CRp	Complete remission with incomplete platelet recovery
CRF	Case Report Form
CMMoL	Chronic Myelomonocytic Leukemia
CTCAE	Common Terminology Criteria for Adverse Events
d	day
DEHP	di(2-ethylhexyl)phthalate
dL	deciliter
DSMB	Data and Safety Monitoring Board
DSPG	Distearoylphosphatidylglycerol
DSPC	Distearoylphosphatidylcholine
EC	Ethics Committee
ECG	Electrocardiogram
ECOG	Eastern Cooperative Oncology Group
EFS	Event-free Survival
ELN	European LeukemiaNet
EOI	End of Infusion
FDA	Food and Drug Administration
FISH	Fluorescence in situ Hybridization
g	gram(s)

---

GCP	Good Clinical Practice
HCl	Hydrogen Chloride
HIPAA	Health Information Protection and Portability Act
HIV	Human Immunodeficiency Virus
HMA	Hypomethylating Agent
HOVON	Hemato-Oncologie voor Volwassenen Nederland
HP	High Purity
HSCT	Hematopoietic Stem Cell Transplantation
ICF	Informed Consent Form
ICH	International Committee on Harmonization
ITT	Intent-to-treat
IRB/EC	Institutional Review Board/Ethics Committee
iv, IV	intravenous
K-M	Kaplan-Meier
L	liter
LDH	Lactate Dehydrogenase
LVEF	Left ventricular ejection fraction
$m^2$	square meters
MDR	Multi-drug Resistance
MDS	myelodysplastic syndrome
MedDRA	Medical Dictionary for Regulatory Activities
mg	milligram(s)
mL	milliliter(s)
MLL	Mixed Lineage Leukemia
MPN	Myeloproliferative neoplasm
MLS	Morphologic Leukemia-free State
MRU	Medical Resource Usage
MTD	Maximum Tolerated Dose
MUGA	Multiple Gated Acquisition scan
mw	molecular weight
N	Number, Population
NF	National Formulary
OS	Overall Survival
PD	Persistent Disease
PhEur	European Pharmacopoeia
PHI	Protected Health Information
PK	Pharmacokinetics
PS	Performance Status
q.s.	quantum sufficiat
RBC	Red blood cells
SAE	Serious Adverse Event
SD	Standard deviation
sAML	Secondary AML
$T_{1/2}$	Half-life
t-AML	Therapy-related AML
Tmax	Time of occurrence of Cmax

u	Units
$\mu$ L	Microliter
ULN	Upper Limits of Normal
USP	United States Pharmacopeia
V	Volume
WHO	World Health Organization

---

## 1 General Information

This document is a protocol for a human research study. This study is to be conducted according to United States and international standards of Good Clinical Practice (FDA Title 21 parts 11, 50, 54, 56, 312, International Conference on Harmonization and the Declaration of Helsinki), applicable government regulations and Institutional research policies and procedures.

## 2 Background Information

### 2.1 Acute Myeloid Leukemia in the Elderly and its Treatment

Acute Myeloid Leukemia in older patients is a poor prognosis disease. While progress in supportive care, such as better antibiotic and antifungal therapy, have improved outcomes for younger persons with this disease, the overall survival of older patients has not changed through the years. The reasons for the poorer prognosis of elderly patients are multifocal and include disease biology, comorbid illness, geriatric syndromes and social factors. Intensive treatment and consolidation chemotherapy can be difficult to administer to an older population. The intensiveness of treatment can be difficult to tolerate in older patients with other comorbid illnesses and geriatric syndromes. Physicians may modify doses to standard regimens to decrease presumed toxicities and inadvertently decrease the efficacy of treatment. Once patients have recovered from induction chemotherapy, they may be too weak to withstand subsequent cycles of consolidation therapy and never achieve a deep, MRD negative, response to treatment and a durable response to therapy.

### 2.2 CombiPlex® Technology and CPX-351

Combination chemotherapy regimens have traditionally been designed empirically on the basis of tolerability. However, *in vitro*, where the ratio of drugs used in combination can be controlled, it has been demonstrated that drug combinations providing synergy at one ratio may be simply additive or even antagonistic at other ratios. When individual free drugs are administered, each agent is handled differently by the body, resulting in varying distribution of the individual drugs to tumor sites which can result in drug ratios that are suboptimal or ineffective. Jazz's technology is based on the findings that *in vitro* synergistic activity of antineoplastic drugs depends on specific drug ratios and that the *in vivo* activity of a combination depends on maintaining the synergistic ratio. In this way, the development of a particular chemotherapeutic regimen can be based on the most efficacious ratio rather than empirically based on toxicity.

The development of CPX-351 (cytarabine:daunorubicin) Liposome Injection was based on 1) defining a synergistic ratio of the two active moieties, cytarabine and daunorubicin, using cell-based screening assays and 2) designing a liposomal drug carrier to maintain this ratio after intravenous administration. This ratio was not based on the empirically-derived, toxicity-guided regimens currently used for cytarabine and anthracyclines.

CPX-351 is a liposomal formulation of a fixed combination of the antineoplastic drugs cytarabine and daunorubicin. The two drugs are present inside the liposome in a 5:1 molar

ratio. The liposome membrane is composed of distearoylphosphatidylcholine, distearoylphosphatidylglycerol and cholesterol in a 7:2:1 molar ratio. These liposomes have a nominal diameter of approximately 100nm and are suspended in sucrose. Sterilization is achieved by filtration through a 0.22  $\mu$ m filter.

CPX-351 is provided as a sterile, pyrogen-free lyophilized formulation in 50 mL glass, single-use vials. Each vial contains 100 units of CPX-351 where each unit contains 1.0 mg cytarabine and 0.44 mg daunorubicin base in liposomes. The lyophilized cake is reconstituted with sterile water for injection to obtain a homogeneous dispersion at 5 units/mL. The composition of the formulation after reconstitution is listed in Table 1 below.

**Table 1: Quantitative Composition**

Component	mw	Amount per Vial	Amount per unit
Cytarabine, USP/PhEur	243	100 mg	1.0 mg
Daunorubicin HCl USP/ PhEur (reported as the free base)	528	44 mg	0.44 mg
Distearoylphosphatidylcholine	790	454 mg	4.5 mg
Distearoylphosphatidylglycerol	801	132 mg	1.3 mg
Cholesterol, HP	387	32 mg	0.3 mg
Copper gluconate, USP	454	92 mg	0.9 mg
Triethanolamine, NF	149	7 mg	0.07 mg
Sucrose, NF	342	2054 mg	20.54 mg

### 2.3 CPX-351 Product Label

CPX-351 (cytarabine:daunorubicin) LIPOSOME FOR INJECTION	100 units/Vial
Each unit contains 1.0 mg ( $\pm 10\%$ ) Cytarabine and 0.44 mg ( $\pm 10\%$ ) Daunorubicin (base) in liposomes containing DSPC, DSPG and cholesterol. Also contains copper as copper gluconate, triethanolamine and sucrose.	
Store refrigerated at 5°C (<math>\pm 3^\circ\text{C}</math>) in an upright position.	
FRAGILE: Do not drop	
Caution: New Drug – Limited by Federal Law to Investigational Use	
Manufactured for Jazz Pharmaceuticals, Inc., [name]	
Lot #	Expiration Date:

### 2.4 Rationale for CPX-351 use in Patients suitable for non-intensive therapy

Three clinical studies have been completed with CPX-351 and a detailed presentation is available in the Investigator's Brochure. A brief summary of observations pertinent to treatment of AML patients, particularly those with co-morbidities and patients whose age tends of limit treatment to non-intensive regimens is discussed below.

The rationale for using CPX-351 to treat older patients thought to be unsuitable for treatment with intensive chemotherapy is rooted in the characteristics of AML in older patients, the pharmacology and mechanism of CPX-351 action, and clinical observations

of the dose-response and safety of CPX-351. It is well known that both the incidence of AML and the risk of AML resistance to chemotherapy increase in an age related manner. Younger patients, particularly those younger than 45 years of age, have higher response rates, lower rates of primary refractory disease, and longer survival than patients over the age of 70. This is associated with an age related rising risk of adverse cytogenetics and multidrug resistance phenotype. CPX-351 packages cytarabine and daunorubicin within liposomes at a 5:1 molar ratio, found *in vitro* to maximize drug synergy and minimize antagonism. CPX-351 liposomes are stable and persist in the plasma for extended periods of time leading to cytarabine and daunorubicin half-lives of approximately 24 hours. This result suggests that CPX-351 may be effective for both in rapidly and slowly cycling leukemias. Exposure of leukemia cells from cell lines and circulating blast cells from patients demonstrate direct entry of CPX-351 liposomes and subsequent intracytoplasmic release of drug. These observations suggest that effective treatment may be possible even in patients with multidrug resistance phenotype due to increased P-glycoprotein expression. Clinical observations of CPX-351 safety and efficacy come almost exclusively from patients considered fit for intensive chemotherapy and indicate a safety profile that is very similar to that of 7+3 chemotherapy except for more prolonged myelosuppression. In the clinic the dose-toxicity/response curve appears to be shallow with most of the grade 3/4 adverse events associated with prolonged myelosuppression rather than severe non-hematologic toxic events.

Taken together these findings suggest that treatment at the MTD (100 units/m^2/dose on day 1, 3, and 5) is likely to be feasible, even in patients of advanced age and with some comorbidities because the toxicities of treatment are mostly confined to myelosuppression and because supportive care with anti-infective prophylaxis is effective. It is thought that full dose treatment is likely to maximize the probability of response and that response is possible even in patient populations enriched for adverse cytogenetics and multi-drug resistance phenotype. The mode of action of CPX-351 should enable rapid clearance of leukemia from the peripheral blood and bone marrow with most patients achieving complete response after one induction course of treatment with recovery from neutropenia usually within 5-7 weeks.

Treating an AML patient population usually considered suitable for non-intensive regimens with CPX-351 is not without risk. This patient population is expected to be older with some baseline comorbidities and cannot be expected to be as resilient as the fit older population treated in Phase II with CPX-351. In that study induction mortality was assessed at Day 30 and 60 and a lower rate of early mortality was observed for CPX-351 treated patients (4/85, 4.7% vs. 6/41, 14.6% at 60 days, *p*=0.053). This result is the best evidence that CPX-351 treatment at full dose is likely to be acceptably safe and suggests that rapid clearance of leukemia due to full dose treatment may assist in reducing the contribution of leukemia to the early death rate.

The greater myelosuppression and more prolonged neutropenia following CPX-351 treatment was associated with a higher frequency of febrile neutropenia (63.5% vs. 51.2%), grade 3 and 4 infections (e.g. bacteremia (42.4% vs. 22%)), and bleeding events (e.g. epistaxis (36.5% vs. 19.5%)). In spite of this the lower mortality rate at 30 and 60 days

indicates that CPX-351 was safe and strongly suggests that anti-infection prophylaxis was effective in preventing infection-related deaths in spite of risks of myelosuppression.

Most recently, a phase 3 trial comparing CPX-351 to standard induction chemotherapy with daunorubicin and cytarabine in older patients aged 60-75 with high risk AML was completed. The Phase 3 trial compared to the standard of care regimen of cytarabine and daunorubicin known as 7+3.

The median overall survival for patients treated with CPX-351 in the study was 9.56 months compared to 5.95 months for patients receiving 7+3, representing a 3.61 month improvement in favor of CPX-351. The hazard ratio (HR) was 0.69 (p=0.005) which represents a 31% reduction in the risk of death versus 7+3. The percentage of patients alive 12 months after randomization was 41.5% on the VYXEOS arm compared to 27.6% on the 7+3 arm. The percentage of patients alive 24 months after randomization was 31.1% on the CPX-351 arm compared to 12.3% on the 7+3 arm.

Event-free survival was also statistically significant in favor of CPX-351. The HR was 0.74 (p-value=0.021). The median event-free survival was 2.53 months in the CPX-351 arm compared to 1.31 months in the 7+3 arm.

CPX-351 also demonstrated a statistically significant improvement in induction response rate (CR+CRi of 47.7% versus 33.3%; p=0.016) and this significance was maintained for the analysis of CR alone (CR of 37.3% versus 25.6%, p=0.040).

Thirty-four percent of CPX-351 treated patients received a stem cell transplant (SCT) compared to 25% of 7+3 treated patients. In a landmark survival analysis of patients receiving a SCT, CPX-351 patients had significantly improved survival post-transplant (HR was 0.46 (p-value=0.0046)). The median overall survival had not been reached in the CPX-351 treated patients compared to 10.25 months in the 7+3 treated patients.

Thirty-day and sixty-day all-cause mortality favored CPX-351. Thirty-day mortality was 5.9% compared to 10.6% and sixty-day mortality was 13.7% versus 21.2%.

Grade 3-5 non-hematologic and hematologic adverse events were similar between the VYXEOS and 7+3 arms.

On the basis of the phase 3 trial data, CPX 351 was approved by the FDA for treatment of older patients aged 60-75 with prior myeloid hematologic disease.

## **2.5 Rationale for Assessment of Non-Hematologic Factors that Influence Outcome in Older AML Patients**

Treatment outcome of older AML patients is closely linked to the age of the patient. Data from the Swedish Acute Leukemia Registry confirms that patient outcome worsens with increasing age. Presumably, the older the age of the patient, the more complicated the disease: the biology of the disease is more severe in the elderly and patients have more

difficulty tolerating the consequences of chemotherapy treatment. Determining the fitness of an older patient for chemotherapy treatment can be quite challenging. The biologic age of an older person may differ significantly from the numeric age: there can tremendous variability in the fitness and function of older people at any given chronologic age after age 60. There is no scientific algorithm to assess the actual biologic age of an older adult. Adverse disease related prognostic factors are more easily measured. Older patients are much more likely to have adverse cytogenetics and unfavorable molecular mutations. Older patients have a higher rate of multi-drug resistant phenotypes and antecedent hematologic disorders. The patient-specific prognostic factors such as severity of comorbid illness, fitness and social support are more difficult to quantify. Many older patients have comorbid illnesses that may or may not be apparent at the time of leukemia diagnosis. Drug metabolism is different in older patients and is influenced by diminished renal and hepatic function that also may not be clinically apparent at the time of diagnosis. The elderly have deficits in immune function that make the tolerance of infections less robust. Patients often have diminished physical conditioning and endurance that may not be visible on routine physical examination. In addition, numerous psychosocial factors influence the outcome of older adults with AML including cognitive decline, social isolation, and lack of a caretaker. The patient-related prognostic factors are more difficult to measure and their significance may not emerge until after treatment for their leukemia has already been given.

Through using the Comprehensive Geriatric Assessment (CGA) to evaluate elderly patients with AML, studies have shown that there appears to be a relationship between cognitive function and outcome in older patients treated for AML. This study will explore this relationship further by implementing cognitive testing to determine this relationship in patients treated with CPX 351. Klepin et al. conducted a study of 74 older AML patients treated with intensive daunorubicin/cytarabine induction and used the CGA to assess patients for chemotherapy fitness. This study demonstrated that impaired cognition (defined as <77 by the Modified Mini-Mental State Exam) and impaired objective physical function (defined as an SPPB<9) predicted a worse overall survival in older adults with AML. [name] et al. (unpublished data) completed an analysis using the CGA to predict overall survival in patients aged 60 or older receiving induction therapy for AML with either standard induction with daunorubicin and cytarabine or low intensity induction with decitabine. One hundred and twenty-six patients were enrolled. Cognitive function as measured by the Blessed Orientation-Memory-Concentration Test. Patients with impaired cognitive function had worse overall survival in univariate analysis but in multivariate analysis this variable lost significance. A small percentage of patients with normal cognitive function on the Blessed Test were given the Montreal Cognitive Assessment and were impaired by measurement on this test. The Blessed may not have been sensitive enough to stratify the cognitive deficits in the population tested. Alternatively, the level of family and social support given to these patients may be more important than cognitive function in the survival of older patients with AML. Given that Klepin's analysis of patients suggested that cognitive function is important to the survival of older patients with AML and that more sensitive testing may be needed to determine the level of cognitive impairment in this population, cognitive testing using both the Blessed and the MOCA will be used in this study to determine whether this is an important factor in the survival of older patients with AML.

### 3 Study Objectives and Rationale

#### 3.1 Primary Objectives

- To assess the feasibility of CPX-351 as first intensive therapy in elderly (age  $\geq 60$  years) patients with AML based on safety and efficacy and to evaluate cognitive function in these patients and its relationship to outcome. CPX-351 alone will be declared feasible if one or two induction courses (3 doses or 5 doses) can be delivered to patients with acceptable 30-day mortality. The primary efficacy endpoint will be overall survival (OS). The primary safety endpoint will be early mortality defined as 30-day mortality.

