## 4.3 Induction

Following registration, patients will be monitored closely for response and safety. Depending on the type and extent of response as well as toxicity, the patient may continue on to consolidation therapy, receive a second induction, or be discontinued from the Treatment Phase and monitored in the Follow-up Phase.

Dosing for first induction: CPX-351 alone

- CPX-351 at 100u/m^2 will be administered on study days 1, 3 and 5

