## 4.4 Repeat of Induction

Patients achieving aplasia/hypoplasia (<5% blast count) will not receive second inductions. Patients with reduced tumor burden and evidence of persistent leukemia who remain fit for additional intensive chemotherapy can be given second inductions up to 60 days (measured from day 1 of chemotherapy treatment) after the first induction treatment date.

Patients unable to achieve a response (CR, CRp, or CRi) after up to 2 inductions are discontinued from further treatment and followed for survival.

Dosing for second induction:

- CPX-351 at 100 u/m^2 will be administered on days 1 and 3

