## 14 APPENDIX 1: Patient Evaluation Flow Sheet – Treatment Phase

Each INDUCTION and CONSOLIDATION:

Day:	Screening	1	2	3	4	5	6	7	10	14	21	28	35	42	Weekly  ±2	150  ±10	End of Phase/Early Term. ±30
Informed Consent 	x																
Medical/Leukemia History	x																
Physical Exam	x							x		x							
Vital Signs	x							x		x							
ECOG Performance Status	x																
ECG	x														x	x 	
Registration	x																
Hematology	x		x					x		x	x	x	x	x	x	x	
Biochemistry	x		x				x	x		x	x	x	x	x	x	x	
Urinalysis	x																
Bone Marrow Evaluation	x														x 	As needed to confirm response/persistence	
Chest X-ray/Chest CT	x																
Echocardiography/MUGA/cardiac MRI	x														x	x	x
Blessed Orientation Concentration															x 	x 	
MOCA	x 							x 							x 	x 	
FACT-Leu	x 							x 							x 	x 	
Response Assessment											x 						
Cytogenetics/Molecular Studies	x																
Adverse Events																	
Concomitant Medications																	
Treatment Administration	CPX-351														x		

The first induction may end prematurely if a second induction is necessary, see Section 4.4. The schedule of evaluations for the first induction is followed until the second induction starts, then the evaluations are followed as indicated in the flow sheet, beginning with Day 1

Second inductions and consolidations of are CPX-351 on Days 1 and 3, see Sections 4.4 & 4.5, See Section 7 for an alternative consolidation regimen of intermediate dose cytarabine, e.g. for patients that exceed 500mg/m^2 cumulative daunorubicin-equivalent dose, or as decided by the investigator

Continue weekly evaluations until confirmation of response (CR/CRi) or persistent disease is declared

Within 30 days prior to start of screening, if informed consent was collected, 30 days elapse and the patient is still not screened he/she must sign another ICF  
Required after first induction (in case the Day 14 bone marrow is non-evaluable or assessment of aplasia is equivocal, a repeat evaluation may be performed 5-14 days later, at the discretion of the treating physician, in order to determine effect and need for second induction

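### Section 3.1 judges delivery of one or two induction courses on 30-day mortality, a window that never holds a full 30 days after dose 4 and holds none of them once the second course starts from about Day 31

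*Combined protocol and SAP*

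**What the plan says.** The only explicit feasibility criterion is in Section 3.1: CPX-351, given as a single agent, "will be declared feasible if one or two induction courses (3 doses or 5 doses) can be delivered to patients with acceptable 30-day mortality". That section also states: "The primary safety endpoint will be early mortality defined as 30-day mortality". It puts no number on what is acceptable.

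In the first induction the drug "will be administered on study days 1, 3 and 5" (Section 4.3). In the second it "will be administered on days 1 and 3" of that course (Section 4.4). Eligible patients whose leukaemia persists "can be given second inductions up to 60 days (measured from day 1 of chemotherapy treatment) after the first induction treatment date" (Section 4.4). No earliest day is laid down, but Appendix 1, footnote 5, ties the decision to the Day 14 marrow: "in case the Day 14 bone marrow is non-evaluable or assessment of aplasia is equivocal, a repeat evaluation may be performed 5-14 days later".

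The synopsis lists "Induction Mortality: assessed at Day 30 and 60; therapies may be changed after 30 days". Section 11.4 plans Kaplan-Meier estimates of mortality at both 30 and 60 days. Section 3.1 uses only the first of these for feasibility.

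**The concern.** The criterion covers delivery of three or five doses, yet its single outcome is fixed early in each patient's course. Doses 4 and 5 come late in that window or after it. A patient who starts a second induction on Day 35 and dies from it is a 30-day survivor, and so counts in favour of feasibility.

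Section 2.4 describes the drug's toxicity as mainly myelosuppression, with neutrophil recovery usually taking 5 to 7 weeks. The period of risk after a second course can therefore run well beyond Day 30. At stake is whether the primary safety result can support a conclusion about two-course delivery, or only about the first course.

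**Working it through.** **The plan's own figure.** Section 11.2 says that the one-sided 95% exact interval for 30- or 60-day mortality has a maximum width below 19% with 30 patients. Clopper-Pearson limits for x = 0 to 30 out of 30 give a largest distance from estimate to one-sided upper limit of 16.6% (at x = 11), and a largest two-sided 95% half-width of 18.7%. Both are under 19%, so the figure stands. It describes the rate in all 30 patients, not in those given a second course.

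**Which clock.** No section defines the origin of the 30 days. The synopsis names Day 30 and Day 60. The interim check in Section 4.2 asks for at least 30 days of follow-up in treated patients. Section 11.4 uses Kaplan-Meier methods, and overall survival starts at registration (Section 8.2), which precedes the first dose by at most 72 hours (Section 7). So there are two candidate origins, Day 1 or up to 3 days earlier, and neither restarts at the second course.

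**Days left after dose 4.** Let s be the study day of dose 4. A 30-day window from Day 1 ends on Day 31, so max(0, 31 − s) days remain. From registration 3 days earlier, max(0, 28 − s) remain. For the 60-day rate the expressions are max(0, 61 − s) and max(0, 58 − s).

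| Dose 4 on | 30-day window, from Day 1 | 30-day window, from registration | 60-day window, from Day 1 | 60-day window, from registration |
|---|---|---|---|---|
| Day 6 (theoretical minimum) | 25 | 22 | 55 | 52 |
| Day 14 (marrow) | 17 | 14 | 47 | 44 |
| Day 19 (earliest repeat marrow) | 12 | 9 | 42 | 39 |
| Day 28 (latest repeat marrow) | 3 | 0 | 33 | 30 |
| Day 31 | 0 | 0 | 30 | 27 |
| Day 42 | 0 | 0 | 19 | 16 |
| Day 60 | 0 | 0 | 1 | 0 |

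Even the theoretical minimum leaves under 30 days. From about Day 31 (Day 28 if counted from registration) the second course lies wholly outside the 30-day window. The 60-day rate gives a full 30 days after dose 4 only if dose 4 is given by about Day 31 (Day 28 from registration).

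**Horizon needed.** With a start 60 days after Day 1, 30 days after dose 4 ends at 60 + 30 = 90 days. Thirty days after dose 5 ends at 62 + 30 = 92 days.

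**Deaths after Day 30 in general.** Section 2.4 reports for the phase 3 trial, CPX-351 against 7+3: "Thirty-day mortality was 5.9% compared to 10.6% and sixty-day mortality was 13.7% versus 21.2"%. For CPX-351 the difference is 13.7 − 5.9 = 7.8 percentage points between the two dates. This is all-cause mortality in a whole treatment arm and is not split by number of induction courses.

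**The case against.** The best defence has four parts.

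- **Any fixed landmark leaves out later treatment.** Thirty-day mortality also matches the benchmarks in Sections 2.4 and 4.2. This is a good reason to keep it as the primary safety endpoint, but not to extend its conclusion to five doses.
- **Section 3.1 makes one declaration about CPX-351, with one or two courses as needed, and the wider objective includes overall survival.** That is a fair reading: there is no separate five-dose claim. The sentence still names both courses and attaches one mortality measure to them.
- **Later deaths are captured.** The 60-day rate is estimated under the primary analyses (Section 11.4), overall survival counts every death for up to 5 years, deaths are reportable SAEs until 30 days after the treatment period (Section 9.2.2), and the DSMB reviews cumulative data twice a year (Section 11.7). All of this stands and lowers the severity. A reader might infer that second-course deaths go unrecorded; they do not. They simply do not enter the feasibility criterion.
- **The remedy is imprecise and has no threshold.** If 5 to 10 patients received a second course (an assumption) and none died, the exact two-sided 95% upper limit would be 1 − 0.025^(1/5) = 52% or 1 − 0.025^(1/10) = 31%. This stands too. The missing threshold applies equally to the 30-day rate, and the small denominator is a reason to report the result as imprecise or to narrow the claim.

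The single clock is an inference. The concern would fall away if the 30 days were counted anew from each course, but no section says so.

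**Conclusion.** The concern holds, as a point worth fixing rather than one that undermines the trial. Under either origin that the documents support, the criterion sees at most part of the 30 days after dose 4: about 17 days for a Day 14 start, about 3 for Day 28, none from about Day 31, and up to 3 days fewer if counted from registration. The 30-day rate therefore cannot carry a conclusion about two-course delivery.

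Three stronger readings are tempting and are not supported.

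- The Day 60 allowance is not why every two-course patient falls short. Dose 4 always follows Day 5, so fewer than 30 days remain whatever the upper limit. The allowance adds only that some second courses fall entirely outside the window.
- The phase 3 rates do not measure the gap. One could compute 7.8/13.7 = 57% of 60-day deaths after Day 30, or 30 × 0.078 = 2.3 deaths in this trial. Those deaths include one-course patients and deaths from leukaemia. The documents give no second-induction rate and no mortality after a second course, so the number missed cannot be estimated.
- Nothing here bears on the accrual-stopping rules, sample size, alpha or power.

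**What to change.** State the origin of the 30-day clock, and keep 30-day mortality as the primary safety endpoint for the first course. Then amend Sections 3.1, 11.1.1 and 11.4 so that the feasibility statement also rests on:

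- the 60-day mortality that Section 11.4 already estimates; and
- for patients given a second induction, deaths within 30 days counted from Day 1 of that course, shown as n/N with the Clopper-Pearson interval that Section 11 already names, and described as imprecise because the denominator will be small.

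The 60-day rate alone would not be enough, since it misses most of the 30 days after a late second course. If the sponsor prefers not to add these, the alternative is to limit the feasibility claim in Section 3.1 to one induction course.

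The cost is wording in three sections and one extra table. The overall survival analysis already needs the death dates. The downsides are a less favourable early-mortality figure and a wide interval for the second course. No dose, schedule or sample size changes.
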